8.2 OBJECTIVES

The primary objectives for this study are as follows:

- To characterize and estimate the frequency of AESIs among participants with PNH exposed to crovalimab. AESIs are as follows:
 - Serious infections

- Meningococcal infection and other infections with encapsulated bacteria
- Development or worsening of any neurological condition (e.g., axonal neuropathy, multifocal mononeuropathy)
- Malignancies and hematologic abnormalities
- Serious hemolysis
- Transient immune complex reactions
- Infusion and injection-related reactions
- To characterize and estimate the frequency of AEs, SAEs, pregnancy outcomes, and infant outcomes in participants with PNH exposed to crovalimab during pregnancy and through breastfeeding. Specifically:
 - To estimate the frequency and further characterize all AEs, adverse pregnancy outcomes, and birth outcomes (during pregnancy until date of delivery), in pregnant female participants with PNH
 - To estimate the frequency and further characterize adverse fetal/neonatal/infant outcomes (e.g., major and minor congenital malformations, gestational age, postnatal growth and development) and SAEs at birth and through at least the first year of life of infants of mothers exposed to crovalimab during pregnancy
 - To estimate the frequency and further characterize all AEs for lactating females and infants exposed to crovalimab through breastfeeding

The secondary objectives for this study are as follows:

- To estimate the frequency and further characterize AEs and SAEs (not included as AESIs) in all participants with PNH exposed to crovalimab.
- To characterize clinical outcomes and laboratory test results relevant to PNH disease among participants with PNH who experienced an AESI
- To characterize patient-reported outcomes (PROs) among participants with PNH who experienced an AESI via a patient-reported fatigue assessment using the Functional Assessment of Chronic Illness Therapy (FACIT)-Fatigue questionnaire

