9.2 SETTING

This study will analyze individual patient-level data gathered from multiple countries within the Crovalimab Silo. To date, the Crovalimab Silo plans to enroll participants from

Belgium, Canada, France, Germany, Italy, Netherlands, South Korea, Spain, United Kingdom, and the United States. China is under feasibility.

Index Date

The index date is defined as follows:

- To evaluate AESIs and other SAEs and AEs for all participants with PNH, the index date will be defined as the date of enrollment in the Crovalimab Silo.
- To characterize SAEs and AEs for women who are pregnant and pregnancy outcomes, the index date for these outcomes will be defined based on the pregnancy status at the time of silo enrollment. If the participant with PNH is pregnant, the index date will be the date of the silo registry enrollment. If the participant with PNH becomes pregnant after enrollment, the index date will be defined as the date of conception (DOC).
- To assess adverse fetal/neonatal/infant outcomes, SAEs, and AEs at birth and through at least the first year of the infant's life, the index date will be defined as the date of infant birth.
- For breastfeeding-related safety events, the index date will be defined as the date of initiation of breastfeeding for women who are in the Crovalimab Silo before breastfeeding starts or as the date of enrollment for women who join the Crovalimab Silo while breastfeeding.

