9.2.2 Inclusion/Exclusion Criteria

To evaluate AESIs and other SAEs and AEs for all participants with PNH:

Participants with PNH included in the SDU study will meet the same inclusion and exclusion criteria from the Crovalimab Silo listed below:

- Inclusion criteria:
 - Participants with PNH confirmed by flow cytometry.
 - Participant and/or parent/legally authorized representative provide written informed consent/assent to participate in the Core Registry and the Crovalimab Silo prior to any registry-related data collection, in a manner approved by the Institutional Review Board (IRB)/Independent Ethics Committee (IEC) and local regulations.
 - Participants with PNH currently being treated with or who start crovalimab during the study period.
- Exclusion criteria:
 - Participants with PNH participating in an interventional PNH clinical trial while receiving crovalimab (i.e., in combination with other therapy), with exception of

participants with PNH participating in the extension period of COMMODORE/COMPOSER Roche studies and Post Trial Access Programs.

The exclusion criteria for all participants will also be applicable to assess crovalimab exposure during pregnancy, as well as pregnancy, infant, and breastfeeding outcomes.

To evaluate AEs and SAEs during pregnancy and pregnancy outcomes:

The following additional inclusion criteria will be applicable:

- Crovalimab exposure during pregnancy or 9 months before DOC

To evaluate infant AEs and SAEs and infant and breastfeeding outcomes:

The following additional inclusion criteria will be applicable:

- Breastfeeding infant
- Infant younger than 12 months of age

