9.2.3 Participant Follow-up

The follow-up period will be the time period from index date (as defined in Section 9.2.1) until the end of the study or censoring, whichever comes first.

To evaluate AESIs and other AEs and SAEs for all participants with PNH, the date of censoring will be defined as the earliest occurrence of any of the following events:

- Consent withdrawal
- Site termination
- Crovalimab treatment discontinuation¹ (with an extra follow-up period after discontinuation)
- Enrollment into an interventional clinical trial²
- Death

To assess safety events during pregnancy and breastfeeding, including pregnancy and infant outcomes, additional censoring events will be defined:

- Date of delivery (for pregnancy safety and outcomes)
- First year of the infant's life (for safety and infant outcomes)
- On the date when breastfeeding stops or first year of the infant's life (for breastfeeding)

[figure not shown]
¹ For participants with PNH censored due to crovalimab treatment discontinuation, follow-up will continue up to 12 months if the participant does not start a new complement inhibitor or for 12 weeks if the participant starts a new complement inhibitor.

² To preserve the integrity of data collected for any interventional therapy for PNH in clinical studies, as well as to avoid duplicate safety reporting, participant data collection will be paused from the Crovalimab Silo and the Core Registry when participants enroll in an interventional clinical study for a PNH therapy.

Note: Safety events from the mother will continue to be recorded even after pregnancy ends, delivery, or the cessation of breastfeeding. Similarly, infant safety events will also continue to be recorded through their first year of age if breastfeeding is suspended.

Evaluation of pregnancy and infant outcomes during crovalimab exposure will rely on prospectively collected data within the Crovalimab Silo only for participants who enroll into the silo before being pregnant. However, for participants who enroll into the Crovalimab Silo while being pregnant, retrospective data on crovalimab exposure and outcomes will be incorporated into the silo, if such data are available from the Core Registry. Data for participants whose pregnancy outcomes occur before their enrollment in the Crovalimab Silo will not be obtainable. Very few instances are expected in these latter two scenarios due to the timing of drug approvals and site initiations in the Core Registry (see Figure 3).

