9.3 VARIABLES

9.3.1 Variables for All Participants with PNH

9.3.1.1 Crovalimab Exposure

The Crovalimab Silo is an observational study. No study medication will be provided as part of participation. Dosing and treatment duration of crovalimab are at the discretion of the physician in accordance with local clinical practice and local labeling.

Crovalimab exposure will be defined as the duration from the date of silo enrollment until crovalimab discontinuation date, plus 12 months if the participant with PNH does not start a new complement inhibitor or plus 12 weeks if the participant starts a new complement inhibitor. For participants with PNH who enroll into the silo under crovalimab treatment, additional time under crovalimab previous to enrollment will be

evaluated from available data requested at enrollment or from the Core Registry at baseline. Dates of exposure to crovalimab and doses administered will be collected and characterized.

For pregnancy and infant outcomes, exposure is defined as the period from 9 months (Based on the average estimated crovalimab terminal half-life of 53.1 days reported in the studies of crovalimab) prior to the DOC until the date of delivery. For breastfeeding outcomes, exposure is defined as the duration from 9 months previous the start of breastfeeding until the infant's first birthday or the date breastfeeding ends, whichever comes first.

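### The infant criteria omit the protocol's own in-utero exposure window, require breastfeeding, and index infant outcomes at birth with no rule for mothers who join after delivery

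*Protocol*

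**What the plan says.** Section 9.2.2 has two blocks of additional criteria. For pregnancy events and outcomes it requires "Crovalimab exposure during pregnancy or 9 months before DOC". For infant events, infant outcomes and breastfeeding outcomes together it lists only "Breastfeeding infant" and "Infant younger than 12 months of age". Mothers qualify if they are on crovalimab or start it at any time in the study period.

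Two other sections are narrower. The Section 8.2 objective for malformations and infant outcomes runs "through at least the first year of life of infants of mothers exposed to crovalimab during pregnancy". Section 9.3.1.1 states: "For pregnancy and infant outcomes, exposure is defined as the period from 9 months" before conception, ending at delivery.

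On timing, Section 9.2 says that for fetal, neonatal and infant outcomes "the index date will be defined as the date of infant birth". The pregnancy bullet switches to enrollment for women already pregnant. The breastfeeding bullet sets the index "as the date of enrollment for women who join the Crovalimab Silo while breastfeeding". Section 9.7.1 starts time at risk at the index date. Section 9.2.3 adds: "Data for participants whose pregnancy outcomes occur before their enrollment in the Crovalimab Silo will not be obtainable", and expects very few such cases.

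Section 9.7.2 presents all infants together and then by breastfeeding status, yes or no. It has no split by in-utero exposure.

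**The concern.** The eligibility list is what a programmer would use to build the infant analysis set, and it does not match the objective, the exposure definition or the planned subgroups. It leaves open whether an infant exposed only through milk counts for malformations and birth outcomes, and whether a formula-fed infant exposed in utero counts at all.

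The index date raises a separate problem. Section 9.2 foresees mothers joining while breastfeeding and moves the index for breastfeeding events, but leaves the infant-outcome index at birth. An infant that had died before its mother enrolled could not enter as a breastfeeding infant. For those who do enter, time from birth to enrollment is event-free by selection, yet it counts as time at risk.

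These outcomes belong to a primary objective, and Section 9.5 targets only about 25 pregnancies, so each wrongly placed infant is visible in the result.

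**Working it through.** The plan states no figure for this point, so there is none to reproduce. The check sets the sections side by side and then sizes the effect under stated assumptions.

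**Who is in the infant set**

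| Infant | 9.2.2 read literally | 8.2 and 9.3.1.1 | 9.7.2 |
|---|---|---|---|
| Breastfed; mother started crovalimab after delivery | in | out for infant outcomes; in for the breastfeeding objective | would be pooled in all infants if admitted |
| Not breastfed; exposed in utero | out | in | expected in the breastfeeding-no subgroup |

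The literal criteria differ from the exposure definition in both rows, and in the second row from the planned subgroup too.

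**When the clock starts**

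Index is birth (9.2) and time at risk runs from index (9.7.1). In Table 1 as extracted, the infant-outcome row is marked for follow-up and for discontinuation or completion, but not for baseline. For a mother who joins after delivery, the interval from birth to enrollment enters the denominator while her infant's death in that interval cannot enter the numerator.

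**Size of the late-entry effect**

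Inputs: 25 exposed infants followed from birth (assumed, one per pregnancy targeted in 9.5), and *k* infants whose mothers join after delivery (not given, so varied).

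1. Neonatal death is death before day 28 (9.3.2.1.13). If all *k* infants enter after day 28, the proportion is multiplied by 25/(25 + *k*). With enrollment spread evenly over the first year (assumed), (365 − 28)/365 = 92% of them would enter after day 28.
2. For a first-year rate with even enrollment, each late entrant is observed for half a year on average but counted for a full year. With a constant event rate, the factor is (25 + 0.5*k*)/(25 + *k*).

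| *k* | Neonatal-death factor | First-year rate factor |
|---|---|---|
| 1 | 25/26 = 0.96 | 25.5/26 = 0.98 |
| 3 | 25/28 = 0.89 | 26.5/28 = 0.95 |
| 5 | 25/30 = 0.83 | 27.5/30 = 0.92 |
| 10 | 25/35 = 0.71 | 30/35 = 0.86 |

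3. For scale, one event in 25 infants is 4.0%, with a Clopper-Pearson 95% interval of 0.1% to 20.4%. With *k* = 3 it becomes 1/28 = 3.6%. Zero events in 25 gives an upper limit of 1 − 0.025^(1/25) = 13.7%; zero in 28 gives 12.3%. For *k* of 1 to 3 the shift is far smaller than the interval.

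**Size of the breastfeeding restriction**

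The number of non-breastfed infants is not given. If 5 of 25 exposed infants were dropped, the zero-event upper limit would rise from 13.7% to 1 − 0.025^(1/20) = 16.8%. If 10 were dropped, it would be 1 − 0.025^(1/15) = 21.8%.

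**The case against.** The strongest reply is that other sections already supply the missing restriction. The objective and the exposure definition both tie infant outcomes to exposure before delivery. Section 9.2.3 describes infant-outcome evaluation for women who enroll before or during pregnancy, and the sentence on unobtainable data can mean that the infant is missing from numerator and denominator alike. An infant exposed only through milk properly belongs to the study under the breastfeeding objective, so admitting it does not show that it enters the malformation analysis. The two infant bullets also cannot be an exhaustive rule, because they would empty the breastfeeding-no subgroup.

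Most of this stands, and it rules out several stronger readings:

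- A reader might infer that the malformation denominator will contain unexposed infants. The text does not settle that: 9.2.2 permits it, while 8.2 and 9.3.1.1 point the other way.
- A reader might infer that early deaths go unseen in general. They are lost only for infants whose mothers join after delivery; deaths among infants of mothers already enrolled can be recorded.
- A reader might infer a distortion of 20% or more. From the factors above, that needs more than six late entrants per 25 exposed infants (25/31 = 0.81, 25/32 = 0.78), which does not fit the very few that Section 9.2.3 expects.
- A reader might infer that the error always reassures. For malformation and birth outcomes this is not shown: Sections 7 and 9.9.4 associate PNH itself with adverse pregnancy outcomes, so adding infants of mothers with PNH who were unexposed in pregnancy need not pull estimates toward a general-population level.

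The reply does not cure the eligibility list, which is the operative rule and says something else. It also does not supply a late-entry rule for the infant index. The reason given in 9.2.3 for expecting few cases, the timing of approvals and site openings, does not address women who first start crovalimab after a delivery later in the registry.

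**Conclusion.** The concern holds as an internal contradiction plus a missing rule. Section 9.2.2 conflicts with 8.2 and 9.3.1.1 on exposure and with 9.7.2 on breastfeeding. Section 9.2 gives infant outcomes no late-entry rule, although its pregnancy and breastfeeding bullets have one.

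The likely numerical effect of late entry is small. With 1 to 3 late entrants against 25 exposed infants, a neonatal-death proportion is multiplied by about 0.96 to 0.89 and a first-year rate by about 0.98 to 0.95. This rests on three assumptions: one infant per targeted pregnancy, enrollment even over the first year for the rate, and entry after day 28 for neonatal death. The true number of late entrants is unknown. For malformation and birth outcomes the direction of any bias is uncertain.

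The study is descriptive, with no formal testing. The wording should be corrected, ideally before the first data extraction planned for Q1 2026, but the point does not threaten the study.

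**What to change.** - **Section 9.2.2, infant outcomes.** For fetal, malformation, birth and infant outcomes, replace the breastfeeding criterion with maternal crovalimab exposure during pregnancy or in the 9 months before conception, the rule already used for pregnancies. Align the Section 8.2 wording, which names pregnancy only.
- **Section 9.2.2, breastfeeding outcomes.** Keep the breastfeeding criterion for a separate breastfeeding cohort that includes infants exposed only through milk.
- **Section 9.2.** Start infant time at risk at the later of birth and the mother's silo enrollment.
- **Birth and neonatal outcomes.** Count them only for infants whose mother enrolled before delivery, and list the others descriptively.

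The cost is wording in the protocol, carried into the SAP. The dates needed (doses, conception, birth, enrollment) are those the protocol's own exposure and index definitions already rely on. The downside is a slightly smaller denominator for birth and neonatal outcomes.

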9.2.3 Participant Follow-up

The follow-up period will be the time period from index date (as defined in Section 9.2.1) until the end of the study or censoring, whichever comes first.

To evaluate AESIs and other AEs and SAEs for all participants with PNH, the date of censoring will be defined as the earliest occurrence of any of the following events:

- Consent withdrawal
- Site termination
- Crovalimab treatment discontinuation¹ (with an extra follow-up period after discontinuation)
- Enrollment into an interventional clinical trial²
- Death

To assess safety events during pregnancy and breastfeeding, including pregnancy and infant outcomes, additional censoring events will be defined:

- Date of delivery (for pregnancy safety and outcomes)
- First year of the infant's life (for safety and infant outcomes)
- On the date when breastfeeding stops or first year of the infant's life (for breastfeeding)

[figure not shown]
¹ For participants with PNH censored due to crovalimab treatment discontinuation, follow-up will continue up to 12 months if the participant does not start a new complement inhibitor or for 12 weeks if the participant starts a new complement inhibitor.

² To preserve the integrity of data collected for any interventional therapy for PNH in clinical studies, as well as to avoid duplicate safety reporting, participant data collection will be paused from the Crovalimab Silo and the Core Registry when participants enroll in an interventional clinical study for a PNH therapy.

Note: Safety events from the mother will continue to be recorded even after pregnancy ends, delivery, or the cessation of breastfeeding. Similarly, infant safety events will also continue to be recorded through their first year of age if breastfeeding is suspended.

Evaluation of pregnancy and infant outcomes during crovalimab exposure will rely on prospectively collected data within the Crovalimab Silo only for participants who enroll into the silo before being pregnant. However, for participants who enroll into the Crovalimab Silo while being pregnant, retrospective data on crovalimab exposure and outcomes will be incorporated into the silo, if such data are available from the Core Registry. Data for participants whose pregnancy outcomes occur before their enrollment in the Crovalimab Silo will not be obtainable. Very few instances are expected in these latter two scenarios due to the timing of drug approvals and site initiations in the Core Registry (see Figure 3).

Figure 3 Identification of Prospective Data in The Silo Registry for Pregnancy and Infant Outcomes

SDU = secondary data use.

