The treatment options available to patients with PNH differ significantly by country and geographical region. The current standard of care (SOC) for PNH involves complement inhibition, which has significantly improved patient outcomes. Allogeneic hematopoietic stem cell transplantation (HSCT) is a curative option that is available in certain countries but presents significant risks. In countries where complement inhibitors are not currently available, management of patients is mainly through supportive care (Cançado et al. 2021).

Crovalimab, a novel, long-acting monoclonal antibody (mAb) targeting C5, has demonstrated efficacy in reducing hemolysis, improving QoL, and potentially offers a more convenient dosing schedule compared to existing therapies (eculizumab and ravulizumab). Overall, crovalimab has shown a well-tolerated safety profile, similar to that of eculizumab in patients with PNH, both in treatment naïve patients and in patients already on treatment with eculizumab or ravulizumab (Roth et al. 2025; Roth et al. 2024).

However, as crovalimab is a new treatment, comprehensive post-marketing surveillance is essential to fully understand its long-term safety profile and potential risks. This is particularly important given the chronic nature of PNH and the need for long-term treatment.

The most commonly reported adverse events (AEs) with crovalimab treatment are pyrexia, headache, infections, infusion and injection-related reactions (IRRs), injection-related reactions (only affecting crovalimab SC administration) and transient immune complex reaction (TICR), also known as Type III hypersensitivity reaction (affecting only patients switching treatments). Meningococcal infection is an important AE of crovalimab treatment, related to its mode of action.

The European Medicines Agency (EMA) and the U.S. Food and Drug Administration (FDA) have requested additional data on specific safety concerns, including:

- Serious infections: Complement inhibition can increase the risk of infections.

- Meningococcal infections: Infections caused by encapsulated bacteria are of special interest, as patients treated with the current SOC have very high-risk to encapsulate infections.
- Hemolysis after discontinuation: The potential for rebound hemolysis upon treatment cessation is high. Nevertheless, the likelihood that a patient with PNH will discontinue treatment with a complement inhibitor without switching to another similar treatment is low.

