Obstetric history ^g	X		
Pregnancy status, outcome and maternal complications	X	X	X
AEs, adverse fetal/neonatal/infant outcomes and baby complications, including growth and development deficiency ^h		X	X
Breastfeeding information	X	X	X
Vaccination	X	X	X
Fatigue questionnaire ⁱ	X	X	

Data	Baseline (Enrollment Visit) ^a	Follow-up ^b	Participant Discontinuation of Crovalimab/Registr y Completion ^c
------	---	------------------------	--

AE = adverse event; ASEI = adverse event of special interest; FACIT = Functional Assessment of Chronic Illness Therapy; LDH = lactate dehydrogenase; MAVE = major adverse vascular event; PNH = paroxysmal nocturnal hemoglobinuria; SAE = serious adverse event; ULN = upper limit of normal.

- ^a Data from baseline will include information collected in the core and at the enrollment visit.
- ^b Data are expected to be entered in the electronic data capture system approximately every 6 months post-enrollment. Every participant will be followed up during their entire crovalimab treatment and up to 12 months after discontinuation of crovalimab, if they do not start a new complement inhibitor (or 12 weeks if they start a new complement inhibitor).
- ^c After discontinuation from crovalimab, participants with PNH would be followed up for 12 months from the discontinuation date of crovalimab (if they do not start a new complement inhibitor) or up to 12 weeks after discontinuation (if they start a new complement inhibitor).
- ^d Including serious infections, Meningococcal infection, development or worsening of any neurological condition (e.g., axonal neuropathy, multifocal mononeuropathy, etc.), malignancies and hematologic abnormalities, serious hemolysis in participants with PNH who discontinue crovalimab, transient immune complex reactions, and infusion and injection related reactions. Treatment, hospitalizations, outcomes and causality for AESIs, AEs, and SAEs will be also collected.
- ^e Including, but not limited to MAVEs (including thrombosis), packed red blood cell transfusions, breakthrough hemolysis, high disease activity status (evidence of $LDH \geq 1.5 \times ULN$ with any of the following symptoms: fatigue, hemoglobinuria, abdominal pain, shortness of breath, anemia (hemoglobin < 100 g/L), dysphagia, erectile dysfunction, development or worsening of autoimmune disease, bone marrow pathology and hematological disorders, impaired renal function, impaired hepatic function, and death.

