9.7.1 Safety Analyses

No formal statistical testing will be performed. Descriptive statistics will be reported using summary tables and figures (where appropriate). Continuous variables will be summarized using mean, standard deviation, median, range (min–max) and interquartile range. Categorical variables will be summarized using counts and proportions (%).

Additionally, incidence and incidence rate (IRs; in person-years) and their 95% CIs of AESIs, SAEs and AEs will be calculated. The exact 95% CIs will be computed using the Clopper-Pearson method (Clopper and Pearson 1934). For the calculation of IRs, the denominator will be the pooled person-time of all the participants within the cohort. The patient time–at-risk will be calculated from index date until the date of an incident event or censoring, whichever occurs first. All first events occurring during follow-up period will be counted in the total number of events (thus, for each participant, only the first event will be counted) and divided by the total patient-years at risk. In addition, to IRs, incidence proportions will be calculated as proportion of participants with PNH afflicted with each of the AESIs, SAEs, and AEs up to the data extraction date.

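### The 12-week follow-up after stopping crovalimab has no limit on when the new complement inhibitor starts, so read literally it censors a late hemolysis before it happened

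*Protocol*

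**What the plan says.** The post-discontinuation window appears in three places in the protocol.

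- Section 9.2.3, footnote 1, on censoring: "follow-up will continue up to 12 months if the participant does not start a new complement inhibitor or for 12 weeks" if one is started. It does not say from which date the 12 weeks run.
- Section 9.3.1.1, which defines exposure as running to the crovalimab discontinuation date, "plus 12 months if the participant with PNH does not start a new complement inhibitor or plus 12 weeks" in the other case. The 12 weeks are added to the discontinuation date.
- Section 9.3.3, Table 1, footnotes b and c. Footnote c states the anchor outright: "or up to 12 weeks after discontinuation (if they start a new complement inhibitor").

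None of the three says by when the new inhibitor must be started for the 12-week branch to apply.

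Section 9.7.1 takes time at risk "from index date until the date of an incident event or censoring, whichever occurs first", and counts only first events within follow-up.

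Hemolysis after discontinuation is on the list of concerns raised by the regulators in section 7, where the protocol says: "The potential for rebound hemolysis upon treatment cessation is high". It adds that "the likelihood that a patient with PNH will discontinue treatment with a complement inhibitor without switching to another similar treatment is low". Serious hemolysis is a primary event of special interest, and Table 1, footnote d, describes the item to be collected as "serious hemolysis in participants with PNH who discontinue crovalimab".

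**The concern.** Which window applies to a participant depends on something that happens later, and the outcome itself can cause it. A participant who stops crovalimab, takes nothing, has a serious hemolysis at month 4 and is then given a complement inhibitor becomes, by the wording, someone who started a new inhibitor. The assigned follow-up is then 12 weeks from discontinuation, which ended before the hemolysis. The event leaves the numerator, and the person-time from week 12 to the event leaves the denominator. A participant who stays well and starts nothing keeps all 12 months of event-free time.

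This is outcome-dependent censoring with a known direction, downward. It applies equally to any other event after week 12 that leads to a new inhibitor, such as a thrombosis. The study has no comparator (section 9.9.8), so the absolute frequency is the result, and a downward bias cannot cancel in a contrast.

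**Working it through.** **Step 1: the rule applied to three participants who stop crovalimab.**

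| Participant | Window under the literal text | Result |
|---|---|---|
| Starts a new inhibitor at or before week 12 | 12 weeks from discontinuation | Same under the literal and the corrected rule |
| Starts nothing, stays well | 12 months | 12 months of event-free time |
| Serious hemolysis at month 4, then a new inhibitor | 12 weeks from discontinuation | Event falls after censoring and is not counted |

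Only the third kind of participant is mishandled.

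**Step 2: what the documents' own figures give.** The terminal half-life in section 9.3.1.1 is 53.1 days.

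- 12 weeks: 84 / 53.1 = 1.58 half-lives; remaining drug 0.5^1.58 = about 33%.
- 12 months: 365.25 / 53.1 = 6.88 half-lives; remaining drug about 0.8%.
- Part of the 12-month window removed for a late starter: (365.25 − 84) / 365.25 = 77%.

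The protocol states no post-discontinuation hemolysis rate and no figure for this bias, so there is nothing of its own to reproduce.

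**Step 3: illustration under assumptions that are not in the documents.** Take stoppers without an immediate switch, a constant hemolysis hazard λ per year, a share q of hemolyses that prompt a new inhibitor 7 days after onset, and no other reason to start one. Let w = 84/365.25 = 0.230 and d = 7/365.25 = 0.019 years. An event is lost if it falls after w, its new inhibitor starts within 12 months, and it is one of the share q. So

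share of first events counted = 1 − q × [exp(−λw) − exp(−λ(1 − d))] / [1 − exp(−λ)].

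For λ = 0.3 the bracket is 0.9333 − 0.7451 = 0.1882 and the denominator is 0.2592, a ratio of 0.726. With q = 0.5 the share counted is 1 − 0.363 = 64%; with q = 0.8, 42%; with q = 1, 27%. A simulation of 400,000 stoppers per scenario gives the same shares.

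| λ per year | q = 0 | q = 0.5 | q = 1 |
|---|---|---|---|
| 0.1 | 100% | 63% | 26% |
| 0.3 | 100% | 64% | 27% |
| 0.5 | 100% | 65% | 29% |
| 1.0 | 100% | 67% | 34% |

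For λ = 0.3 the estimated rate among these stoppers is 0.30 per person-year at q = 0, 0.20 at q = 0.5, 0.13 at q = 0.8 and 0.09 at q = 1. If follow-up instead ends at the later of week 12 and the actual start, capped at 12 months, the simulation recovers 0.30 at every q.

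**Step 4: starts unrelated to hemolysis.** With q = 0 and a background start rate of 0.3 per year, the literal rule gives 0.299 against 0.300. It counts 92% of the events that the corrected rule counts but leaves the rate unbiased. The bias comes only from starts that the event itself prompts.

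**The case against.** The strongest reply is that no section instructs anyone to remove events retrospectively. At month 4 the example participant has started nothing and is being followed on the 12-month track; section 9.7.1 would close the clock at the hemolysis, before the new inhibitor. On this view the text merely separates switchers from non-switchers and leaves late starters unaddressed. That is a possible intention, and section 9.2.3 alone would allow it. But section 9.3.1.1 and Table 1 tie the 12 weeks to discontinuation and set no deadline for the start, so a programmer following them assigns a censoring date at week 12. Recording the event does not by itself bring it back inside follow-up.

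Other parts of the reply stand.

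- Section 7 expects few participants to stop without switching, so the number of events lost may be small.
- A participant who resumes crovalimab is not clearly starting a new inhibitor.
- Section 9.7.1 defines rates over the pooled person-time of the cohort and specifies no separate post-discontinuation rate. The figures above describe stoppers without an immediate switch, not the cohort rate.

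A reader might also infer, from a third of the drug remaining at week 12, that much of the rebound comes later. The documents give neither a concentration threshold nor any timing of rebound, so they do not support that. Nor do they support any particular ratio of observed to true rate.

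**Conclusion.** The point holds as a defect in the wording of the follow-up rule. As written in section 9.3.1.1 and Table 1, and left open in section 9.2.3, the rule makes the length of follow-up depend on a later event that the outcome can trigger. Applied literally, it under-counts serious hemolysis after discontinuation whenever a hemolysis after week 12 prompts a new inhibitor.

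The direction follows from the text; the size does not. The 26-67% range rests on an assumed constant hazard of 0.1 to 1.0 per year, 50-100% of events prompting a restart, and a 7-day delay. The absolute number of events at stake is probably small, but these few participants are the ones who inform the question about rebound. This is an inexpensive correction worth making, not evidence that the study's overall serious hemolysis rate will be materially wrong.

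**What to change.** Use one rule, in the same words, in section 9.2.3 footnote 1, section 9.3.1.1 and Table 1 footnotes b and c, that depends only on information known at the time. For example: follow-up ends 12 months after crovalimab discontinuation or, if a new complement inhibitor is started earlier, at the later of 12 weeks after discontinuation and the date of that start. Every event before the new inhibitor then counts, and participants who switch by week 12 keep the present window.

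The cost is wording in three places. Until a new inhibitor is started the site cannot know that one will be, so it should already be following on the 12-month track, and no collection beyond that is needed.

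An acceptable alternative runs the short window for 12 weeks from the first dose of the new inhibitor, within the 12-month limit. It would also capture immune complex reactions after a late switch, which section 7 says can occur when moving from crovalimab to another C5 inhibitor. It costs up to 12 more weeks of follow-up on another drug, which should be kept apart from the crovalimab exposure definition, and it would have to be agreed with the registry, which runs the data collection. Either version is best settled before the first data extraction, planned for Q1 2026.
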